#### 9.4.1. Patient Selection

Structured data will be used to screen patients who received treatment within the USON based on the eligibility criteria described in Table 2. The patient attrition will be based on this initial screening.

Study-eligible patients who received first-line AI monotherapy or palbociclib + AI combination therapy will be selected to undergo a targeted chart review. During the course of abstraction, patients' eligibility for the study will be verified and some of these patients may be found to be ineligible. Reasons for disqualification will be captured and reported.

Table 2. Patient Attrition (01 January 2010 - 30 June 2020)

Eligibility criteria	Patient count - excluded	Patient count - remained
Documented diagnosis of hormone receptor-positive (estrogen receptor-positive or progesterone receptor-positive), human epidermal growth factor receptor 2-negative metastatic breast cancer (MBC) who received a qualifying treatment (ie, palbociclib, letrozole, exemestane or anastrozole) within the USON during the study identification period.	-	27,835
Aged 18 years at initial recorded diagnosis of MBC	3	27,832
Exclusion of patients enrolled in an interventional clinical trial during the study observation period.	2,299	25,533
Did not receive a treatment indicated for another primary cancer during the study observation period.	2,548	22,985
Received care at a USON site(s) utilizing the full EHR capacities of iKM at the time of treatment.	0	22,985
Exclusion of patients with qualifying treatments (ie, palbociclib, letrozole, exemestane or anastrozole) received only prior to metastases date and not after advanced diagnosis.	1,143	21,842
Exclusion of patients with start of first regimen more than 120 days after metastases date.	2,345	19,497
Exclusion of patients from sites without USON data access agreement.	8,440	11,057

Initial cohort counts (patients who initiated the cohort - specific regimen in an appropriate LOT)		
Pb-AI: Palbociclib combination therapy with an aromatase inhibitor (letrozole, exemestane, or anastrozole) among patients as first-line therapy in the advanced or metastatic setting. Patients with evidence of prior treatment with other CDK 4/6 inhibitors (ribociclib or abemaciclib), aromatase inhibitors (letrozole, exemestane, or anastrozole), tamoxifen, raloxifene, toremifene, or fulvestrant in the advanced or metastatic setting were excluded.	-	1,524
AI mono: Aromatase inhibitor (letrozole, exemestane or anastrozole) monotherapy as first-line treatment in the advanced or metastatic setting. Patients with evidence of prior treatment with other CDK 4/6 inhibitors (ribociclib or abemaciclib), aromatase inhibitors (letrozole, exemestane, or anastrozole), tamoxifen, raloxifene, toremifene, or fulvestrant in the advanced or metastatic setting were excluded.	-	4,395
Exclusion of patients who initiated qualifying regimens prior to the start of	f the study period (by	cohort)
Pb-AI: aromatase inhibitor (letrozole, exemestane, or anastrozole) + palbociclib.	15	1,509
AI mono: aromatase inhibitor (letrozole, exemestane, or anastrozole) mono.	461	3,934

Table 3. Menopausal Status by Cohort (Based on Structured Data Alone)\*

Status	AI Mono (n=3,934)	PB-AI (n=1,509)
Perimenopausal	50 (1.3%)	12 (0.8%)
Premenopausal	185 (4.7%)	136 (9.0%)
Postmenopausal	2,363 (60.1%)	1,082 (71.7%)
Not documented	1,336 (34.0%)	279 (18.5%)

\* Based on initial feasibility estimate with menopausal status to be confirmed through chart review. Chart review will also examine those patients where menopausal status is "not documented" in the structured field.

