Understanding the effectiveness of new treatments in diverse clinical practice as a complement to RCT data is important as this provides evidence of the clinical benefit of these treatments in a more heterogeneous population with comorbid conditions and variations in care delivery seen in routine clinical practice. Since its approval in February 2015, palbociclib has rapidly become the standard of care in the treatment of HR+/HER2-advanced breast cancer (ABC) and is globally available commercially. Palbociclib has been available for use in the US for over 5 years with over 315,000 patients treated worldwide and nearly 130,000 in the US as of June 2020 making it possible to study comparative effectiveness in a large and diverse US HR+/HER2- MBC population.

Real world (rw) assessment has also been shown to be feasible and meaningful. Analysis of data for patients with MBC has been conducted to show that clinically meaningful information can be derived from the assessment of real-world progression-free survival (rwPFS) and real-world tumor response (rwTR) based on electronic health record (EHR) data abstraction when proper quality controls and analytic methods are incorporated based on concordance shown between RCTs and rw data. Concordance of rwPFS and real world tumor response (rwTR) from the US EHR with RCT data in MBC was recently demonstrated in a retrospective analysis comparing the PALOMA-2 trial letrozole + placebo control arm population cohort with a corresponding real-world cohort of US MBC patients treated with letrozole alone indicating the potential for real-world data to provide clinically consistent outcomes information (Bartlett et al, 2020).

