Endocrine sensitivity	iKM structured data + chart review (derived)	Medical history prior to index	Relapse more than 12 months after completing adjuvant endocrine therapy.
Disease-free interval	iKM structured data + chart review (derived)	Medical history prior to index	Obfuscated dates between discontinuation of adjuvant therapy and the start of treatment for unresectable and/or metastatic disease.
Radiotherapy	iKM structured data + chart review	Medical history prior to index and study observation period	All radiotherapy, along with obfuscated dates, received prior to or during the study observation period will be captured. During analysis, 2 variables will be constructed:  "Concomitant radiotherapy" will be defined as radiotherapies given during 1L treatment  "Prior radiotherapy" will be defined as all radiotherapies prior to index date
Index treatment regimen	iKM structured data + chart review	Study observation period	Patients' index treatment will be categorized based on the cohort descriptions in Section 9.1: Palbociclib combination therapy with an AI (letrozole, exemestane or anastrozole) or AI monotherapy
LHRH treatment	iKM structured data + chart review	Study observation period	LHRH treatment received during the study observation period will be captured.
Date of treatment initiation during the	iKM structured data + chart	Study observation	The obfuscated date of initiation with a palbociclib- based combination regimen or AI monotherapy

Variable	Source(s)	Period of measurement	Operational definition
patient identification period (ie, index date)	review	period	(letrozole, exemestane or anastrozole) during the study identification period. If a regimen consists of more than one drug with drugs given on different dates, the date of the first administration of any drug will be used.
Index treatment end date(s)	iKM structured data + chart review	Study observation period	Obfuscated date of final treatment for each drug or regimen. If a regimen consists of more than one drug with drugs ending on different dates, the date of the last administration of any drug will be used. It is possible that the patient's treatment stop date is not documented if the patient dies, is lost-to follow-up or is still ontherapy. The final treatment date, death date or end of study date will be used, whichever is earliest.

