Index line of therapy (LOT)	iKM structured data	Study observation period	LOT will be operationally defined as a course of care that continues until disease progression or unacceptable toxicity. As such, advancement in LOT will be assigned if there is documented or inferred progression or toxicity.  Switching between aromatase inhibitors (exemestane, letrozole, anastrozole) will not constitute a change in regimen, unless the next aromatase inhibitor is started due to provider-documented progression or toxicity. In contrast, switching between other classes of treatments (eg, CDK 4/6 inhibitors, chemotherapies), will
Number of cycles (index treatment)	iKM structured data	Study observation	constitute a change in regimen.  The number of provider-documented therapy cycles received for the index treatment.
Index treatment schedule (cycle length and frequency)	iKM structured data + chart review	period Study observation period	The planned frequency and cycle length of the index treatment.
Index treatment schedule changes	iKM structured data + chart review	Study observation period	Each index treatment (either AI monotherapy or palbociclib combination therapy) schedule change will be captured and reported, along with the obfuscated date.
Index palbociclib treatment starting dose	iKM structured data + chart review	Study observation period	The actual index treatment starting palbociclib dosage received.  Categories to be presented: 75 mg 100 mg 125 mg Other No information
Palbociclib combination regimen	iKM structured data + chart review	Study observation period	Classification of patients into the following treatment groups: Palbociclib-letrozole Palbociclib-anastrozole Palbociclib-exemestane
Reason for palbociclib dose changes	Chart review	Study observation period	Data for palbociclib dose change reason will exclusively come from chart review. Reviewers will be asked to select reason(s) as explicitly documented in patients' charts.  If available, reason patients discontinued treatment will be abstracted:

Variable	Source(s)	Period of measurement	Operational definition
			Lack of response Patient preference Toxicity Other No information Reviewers will specify other reasons; these will be reported if any represent >5% of patients.

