#### **Information Bias**

Due to the nature of the study design, there is potential for bias to be introduced into the calculations of clinical outcomes. Specifically, patients who initiated treatment during the patient identification period may be meaningfully different from other patients who initiated therapy prior or after the study identification period. To minimize this risk, the study observation period will begin on the date palbociclib was approved for the treatment of metastatic breast cancer so that the study cohorts will both represent the treatment landscape after this approval.

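### Table 2's 15 palbociclib + AI patients dated before the study period are unexplained, and the index rule lets the palbociclib response clock start before palbociclib

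*Protocol*

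**What the plan says.** Protocol 9.4.1 gives the screening counts under the title "Table 2. Patient Attrition (01 January 2010 - 30 June 2020". The final rows are headed "Exclusion of patients who initiated qualifying regimens prior to the start" of the study period. In the row labelled "Pb-AI: aromatase inhibitor (letrozole, exemestane, or anastrozole) + palbociclib", 15 are removed and 1,509 remain. The matching AI monotherapy row removes 461 and leaves 3,934. Neither row states the date used.

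Protocol section 7 says "Since its approval in February 2015, palbociclib has rapidly become the standard of care". Protocol sections 8, 9.1, 9.5 and 9.7.2 all start the period on 01 January 2010. Protocol 9.9.1 (Information Bias) instead says "the study observation period will begin on the date palbociclib was approved for the treatment of metastatic breast cancer".

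For a regimen of several drugs started on different days, Protocol Table 1 sets the index by this rule: "the date of the first administration of any drug will be used". SAP Table 2 keeps it. On lines of therapy, Protocol Table 1 says "advancement in LOT will be assigned if there is documented or inferred progression or toxicity".

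SAP 2.1 treats drugs begun within 60 days of the first as one combination, but only where no intention to combine was documented. It also runs a multi-drug regimen from the earliest start to the latest stop among its drugs. SAP 8.1.2 counts a CR or PR at least 30 days after the cohort regimen began and ignores assessments after PD. Where a first line holds more than one regimen, it restricts assessments to those made on palbociclib plus AI.

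**The concern.** A palbociclib + AI regimen dated before 2010 is implausible if dated by palbociclib, and no text in either document explains the 15. One natural way to obtain such a date is to use the AI start. Nothing in the protocol's index rule limits the interval between the AI and palbociclib.

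If that happens in the analysed cohort, three things follow for a patient who added palbociclib late:

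- Her baseline values are taken around the AI start. They feed the propensity score and hence the IPTW primary analysis.
- She reached palbociclib without a line-ending progression, because progression would have advanced the line. Part of her follow-up is therefore selected for doing well on AI alone.
- A response reached on AI alone can be counted for palbociclib.

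The last two favour the palbociclib cohort. The Table 2 step removes only patients indexed before the period. The same pattern with an AI start inside the period would pass through.

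**Working it through.** **1. Table 2 subtracts correctly.** Palbociclib + AI: 1,524 − 15 = 1,509. AI monotherapy: 4,395 − 461 = 3,934. The upper rows run 27,835 − 3 − 2,299 − 2,548 − 0 − 1,143 − 2,345 − 8,440 = 11,057, as printed. The Table 3 columns sum to 1,509 (12 + 136 + 1,082 + 279) and 3,934 (50 + 185 + 2,363 + 1,336). The problem is one of consistency, not arithmetic.

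**2. The dates do not fit.** The approval month is February 2015; Protocol 9.7.3.4 uses 01 February 2015 for its post-approval subgroup. From 01 January 2010 that is 1,857 days, and 1,857 / 365.25 = 5.1 years.

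**3. Size of the 15.** They are 15 / 1,524 = 1.0% of the cohort at that step. The pre/perimenopausal share in Table 3 is (12 + 136) / 1,509 = 148 / 1,509 = 9.8%. Restoring the 15 would add 15 × 148 / 1,509 = 1.5 patients. If every patient without a documented status also counted, it would add 15 × (148 + 279) / 1,509 = 4.2. The ceiling is 15.

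**4. Candidate explanations.**

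| Explanation | Supports it | Against it |
|---|---|---|
| Index is the AI start | First-dose-of-any-drug rule, no gap limit in the protocol | The palbociclib row of Table 2 already excludes prior AI in the metastatic setting, a step before the 15 |
| Cut was at approval | Protocol 9.9.1 | Four protocol sections say 2010; post-approval patients are only a subgroup, which the SAP drops for too few controls |
| Date errors or pre-approval trial supply | 9.9.1 admits coding errors; Table 2 removes only trial enrolment during the observation period | Nothing in the text confirms it |

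A rough check on the second row: approval falls 5.1 / 10.5 = 48% of the way through the index period (January 2010 to June 2020). If AI monotherapy starts were spread evenly (an assumption), a cut at approval would remove about half of them. The table removes 461 / 4,395 = 10.5%. This weighs against that explanation but does not exclude it, because no calendar-year split is given.

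**5. What the response rule permits.** Let the AI start on day 0 and palbociclib on day *g*. If the regimen starts on day 0, as SAP 2.1 and SAP Table 2 say, a CR or PR counts from day 30. Whenever *g* > 30, the window from day 30 to day *g* is open before any palbociclib.

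- Undocumented intent, combined by the 60-day window: *g* is at most 60, so the open window is at most 60 − 30 = 30 days.
- Documented intent: *g* has no stated limit, so neither has the window.
- AI alone recorded as a separate regimen in the same line: the multi-regimen sentence in SAP 8.1.2 excludes the AI-alone assessments, and the window is closed.

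**6. Effect per patient.** With 116 palbociclib patients in the SAP, one wrongly credited responder moves the unweighted rwRR by 1 / 116 = 0.9 points. In the set with tumour assessments, 116 − 13 = 103, so 1 / 103 = 1.0 point. Under weighting, the effect scales with that patient's weight.

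**The case against.** The case against is substantial. Table 2 is an unverified structured-data screen. The SAP has replaced its projection with 196 chart-verified patients (116 and 80), the 15 were excluded anyway, and no hypothesis is tested. The exclusion of prior AI should already have removed anyone with years of AI alone. It is hard to believe that a documented intention to combine would cover a five-year gap. SAP 8.1.2 refers to the palbociclib plus AI treatment period and, for lines with several regimens, limits assessments to that combination. Checks for logical sequence and implausible dates are already planned in Protocol 9.6 and 9.8.

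Most of this stands, and it disposes of any claim about the planned counts. Two parts do not close the question. First, the prior-AI exclusion was applied in forming the 1,524, so it would miss exactly those patients whose AI had been counted as part of the combination. Second, SAP 8.1.2 protects only if its treatment period is read by palbociclib dates, whereas SAP 2.1 dates a combination from its first drug. Chart review verifies eligibility, but under the same index definition.

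A reader might infer that Table 2 proves the index rule or the period wrong, or that 15 patients are mis-dated by at least five years. The documents do not support either: the row carries no date and several causes remain open. A reader might also assume that 1% to 5% of the 116 are late additions (1 to 6 patients, or 0.9 to 5.2 points). Nothing in the documents supports that share, and the upper figure needs every such patient to be a false responder.

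**Conclusion.** The concern holds in a limited form. The 15 cannot be reconciled with a 2010 start if the date is the palbociclib start, the cause is undetermined, and their direct effect on the planned counts is about 1.5 patients. Protocol 9.9.1 also contradicts the 2010 period used elsewhere.

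What matters for the result is the rule the row draws attention to. As written, the index date and the 30-day clock in the palbociclib cohort can precede palbociclib, without limit where combination intent is documented, and SAP 8.1.2 only partly prevents crediting an AI-alone response to palbociclib. The bias from a wrongly credited response would raise the palbociclib rwRR, by up to 0.9 points per patient (unweighted, full analysis set). This assumes that at least one such patient is among the 116 and has a CR or PR before palbociclib, or within its first 30 days, that she would otherwise lack. The documents do not show how many there are; it may be none.

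**What to change.** - **SAP 8.1.2:** for the palbociclib cohort, count CR or PR only from 30 days after the first palbociclib dose, and only if no PD has occurred since the index date.
- **Edit check:** list every palbociclib-cohort patient with an index date earlier than approval less 60 days (03 December 2014 if 01 February 2015 is used), or with an AI-to-palbociclib gap over 60 days. Report the number. Since Protocol 9.3 allows dates to be coarsened at de-identification, this may have to be run by the data holder.
- **Sensitivity analysis:** repeat the primary analysis without the listed patients, re-estimating the propensity score as SAP 8.2.1 already requires for each population. This keeps the documented-intent exception in the main analysis. Removing it for every patient is debatable, because the documents do not show it to be faulty.
- **Protocol:** state the start date used for Table 2, explain the 15, and reconcile 9.9.1 with the 2010 index period.

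The cost is a small amount of programming on dates already to be collected, one extra analysis, and possibly a slightly lower palbociclib rwRR.

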## 9.5. Study Size

All eligible patients will be included for the primary analysis. Approximately 385 patients will be included with close to a 1:2 ratio between palbociclib + AI and AI alone cohorts based on examination of structured iKM data applying inclusion/exclusion criteria (Table 2 and Table 3) between 01 January 2010 and 30 June 2020 (see Section 9.7.2).

## 9.6. Data Management

The McKesson study team will collaborate with McKesson's Commercial Intelligence group to collect the structured iKM data that will be used for analysis. The Commercial Intelligence team will be provided with a Data Collections Variable List, which will detail the specific data elements that will need to be included in the study dataset. A Data Analyst will begin by generating high-level study sample counts that demonstrate attrition rates of the inclusion/exclusion criteria.

The study team will review the attrition count and the Data Analyst will proceed with collecting the remaining data elements on the Data Collections Variable List. The Data Analyst will perform an initial quality control check of the study dataset before providing the file to the study team's Biostatistician on a secure server. Once received by the Biostatistician, data validation will continue and will consist of, but is not limited to, quality control checks for appropriate values, logical sequences and quantity of missing values.

A list of patients eligible for chart review will be generated by the Data Analyst and the Biostatistician will apply the agreed upon sampling technique to identify the specific patients that will undergo chart review. This list of patients will then be securely transmitted to the Chart Review Team Manager.

The McKesson study team will lead a training session with chart abstractors to discuss study specific considerations. Reference materials will also be provided to abstractors at this time. If chart abstractors have questions during the abstraction process, these will first be raised to the Chart Review Team Manager. If needed, questions can be escalated to the Outcomes Researcher and Principal Investigator.

Chart review will be accomplished by use of a secure, web-based eCRF. The main purpose of the eCRF is to obtain data required by this non-interventional study protocol in a complete, accurate, legible and in a timely manner.

Analyses will be conducted using statistical analysis software (SAS®; SAS Institute Inc., Cary, NC, US) and/or R: A Language and Environment for Statistical Computing (R Foundation for Statistical Computing, Vienna, Austria) as appropriate.

Once on Pfizer servers, Pfizer staff perform a semi-automated process for quality assurance on the data, checking that the metadata align with the data dictionary from USON dataset, the number of records equals that expected from the vendor, and that the data types and controlled vocabularies are correct. The data are then loaded into a secure Pfizer server. Pfizer servers are backed up nightly and have failover and off-site redundancy. Access to data is limited only to Pfizer colleagues and is monitored with all end user activity is logged.

Pfizer maintains copies of all EHR or other real-world data in accordance with the FDA's July 2018 Industry Guidance on Use of Electronic Health Record Data in Clinical Investigations (FDA, 2018),  though Pfizer maintains its data in excess of the guidance – for a minimum of 7 years.

# 9.6.1. Case Report Forms (CRFs)/Data Collection Tools (DCTs)/Electronic Data Record

As used in this protocol, the term CRF should be understood to refer to either a paper form or an electronic data record or both, depending on the data collection method used in this study.

A CRF is required and should be completed for each included patient. The completed original CRFs are the sole property of Pfizer and should not be made available in any form to third parties, except for authorized representatives of Pfizer or appropriate regulatory authorities, without written permission from Pfizer. McKesson shall ensure that the CRFs are securely stored at the study site in encrypted electronic and/or paper form and will be password protected or secured in a locked room to prevent access by unauthorized third parties.

McKesson has ultimate responsibility for the collection and reporting of all clinical, safety, and laboratory data entered on the CRFs and any other data collection forms (source documents) and ensuring that they are accurate, authentic/original, attributable, complete, consistent, legible, timely (contemporaneous), enduring, and available when required. The CRFs must be signed by the investigator or by an authorized staff member to attest that the data contained on the CRFs are true. Any corrections to entries made in the CRFs or source documents must be dated, initialed, and explained (if necessary) and should not obscure the original entry.

The source documents are the hospital or the physician's chart. In these cases, data collected on the CRFs must match those charts.

